CGI-S	Clinical Global Impression of Severity
cm/s	Centimeters per second
CP or CPt	Conventional Physiotherapy
CRA	Clinical Research Associate
CRO	Clinical Research Organization
DT	Dual Task
eCRF	Electronic Case Report Form
EDC	Electronic Data Capture
ePRO	Electronic Patient Reported Outcome
FDA	Food and Drug Administration
FM	FeetMe Rehabilitation
FNA	FeetMe Rehabilitation No Access
FOG	Freezing Of Gait
FOG-Q	Freezing of gait questionnaire
GAD-7	Global Anxiety Disorder Questionnaire
GCP	Good Clinical Practice
H&Y	Hoehn and Yahr staging
HAS	Haute Autorité de Santé
HS	Heel Strike
ICF	Informed Consent Form
IEC	Independent Ethical Committee
IMU	Inertial Measurement Unit
IRB	Institutional Review Board
ISO	International Organization for Standardization
IxRS	Interactive Voice/Web Response System
LARS	The Lille Apathy Rating Scale

2 LIST OF ABBREVIATIONS AND DEFINITIONS OF TERMS

LPLO	Last Patient Last Observation
LSVT	Lee Silverman Voice Treatment
MDS-UPDRS	The Movement Disorder Society sponsored Revision of the Unified Parkinson's Disease Rating Scale
MiniBESTest	Mini Balance Evaluation Systems Test
MoCA	Montreal Cognitive Assessment
NA	Not Applicable
NI	Non Intervention
NSAE	Non-serious Adverse Event
PD	Parkinson's Disease
PDQ-39	Parkinson's Disease Questionnaire
PDQ-8	Parkinson Disease Questionnaire short form
PDSS2	Parkinson Disease Sleep Scale 2
PGI-I	Patient Global Impression of Improvement
PGI-S	Patient Global Impression of Severity
PGI-S	Patient Global Impression of Severity
QIDS SR	Quick Inventory of Depressive Symptomatology, self-report questionnaire
SADE	Serious Adverse Device Effect
SAE	Serious Adverse Event
SAP	Statistical Analysis Plan
SE-ADL	Schwab and England Activities of Daily Living
SoA	Schedule of Assessments
ТО	Toe Off
VAS	Visual Analog Scale

3 SYNOPSIS

SPONSOR:	CLINICAL INVESTIGATIONAL PLAN NUMBER:
FeetMe	
TITLE	A randomised, controlled, open-label, multi-centre study to evaluate the efficacy of FeetMe® home-based rehabilitation program in comparison to conventional physiotherapy in patients with Parkinson's Disease using connected insoles.
ACRONYM	RE-CONNECT
NAME OF DEVICES	FeetMe Monitor (insoles) and FeetMe Rehabilitation (application)
RATIONALE	Parkinson's disease (PD) is characterised by a range of motor- and non- motor symptoms which define the quality of life (QoL) of the PD patients. Physical rehabilitation is an essential part of the care complementing pharmacological treatment and it is recommended by the French Health Authority (Haute Autorité de Santé [HAS]) to support disease management. Despite demonstrated benefits of rehabilitation programs on gait and balance and consequently on risk of falls and QoL, only a fraction of PD patients benefit from conventional physiotherapy (CPt) due to multiple factors including the limited number of practices and rising demand. Thus, identifying an effective rehabilitation program that is readily accessible for PD patients remains a pressing unmet need. FeetMe Rehabilitation is an innovative technology solution that combines connected insoles with a mobile application containing rehabilitation exercises specific for PD patients, focusing on endurance, muscle strength and postural stability. The device is complemented by a remote rehabilitation service provided by a rehabilitation professional to follow progression and to adapt training needs based on results. Since patients can train remotely and in their home environment, FeetMe Rehabilitation ensures equal access to this essential therapy, which is currently strongly limited by local availability of rehabilitation centres and personnel.
	outcome measures of efficacy are defined according to the expected benefits of improving gait and balance, number of falls and QoL.
OBJECTIVES	Primary Objective
	To evaluate the efficacy of FeetMe home-based rehabilitation program compared to conventional physiotherapy at Week 12 in PD patients assessed by gait velocity.
	Key Secondary Objective

	To evaluate the efficacy of FeetMe home-based rehabilitation program compared to conventional physiotherapy at Week 12 in PD patients assessed by stance time variability.	
	Secondary Objectives	
	To evaluate the efficacy of FeetMe home-based rehabilitation program compared to conventional physiotherapy at Week 12 in PD patients assessed by:	
	• rate of falls	
	• standard gait and balance exercises	
	MDS-UPDRS Part III	
	• quality of life	
	Exploratory Objectives	
	• To explore the long-term efficacy of FeetMe home-based rehabilitation program compared to conventional physiotherapy in patients who continue to Week 24.	
	• To explore the maintenance of the effect after 3 months in patients who stop physiotherapy at Week 12.	
	• To explore the efficacy in patients who switch from one treatment to the other at Week 12.	
	• To explore the compliance with training, acceptability, and patient's engagement throughout the study.	
	• To explore the satisfaction with the service.	
	• To explore the safety of FeetMe home-based rehabilitation program.	
PLANNED DURATION	The estimated recruitment period is approximately 18 months. The total duration of the study for each patient will be up to 26.5 weeks divided as follows:	
	• Screening: up to one month	
	• Primary Intervention period: 12 weeks	
	• Long Term Intervention Period: 12 weeks	
	The end of the study is defined as the date when the last participant's last observation (LPLO) occurs, upon completion of the End of Study Visit.	
SITES	6 sites (Nîmes, Nice, Nantes, Toulouse, Lille and Avicennes)	
POPULATION	All patients must fulfil the following criteria:	
	Inclusion criteria	
	1. Written informed consent to participate in the study.	
	2. Male or female patients between 40 to 70 years of age, inclusive.	

	3.	Body weight range of 40 kg to120 kg and a body mass index (BMI) of 18 to 34 kg/m2.
	4.	Diagnosis of Idiopathic Parkinson's disease (PD) according to UK Brain Bank Criteria (2/3 symptoms), with Hoehn and Yahr (H&Y) staging level 2, 2.5 or 3.
	5.	Disease onset of at least 3 years prior to enrolment.
	6.	Patients with a history of 50% of levodopa responsiveness based on motor signs.
	7.	On stable treatment of PD medication for at least 30 days before screening and with no expected major changes during the first 3 months of the study.
	8.	Prescription for physiotherapy available.
	9.	Ability to walk without aid for at least 6 minutes.
	10.	Shoe size between 35 – 46 (European Standard).
	11.	Intact skin on feet.
	12.	Adequate visual and auditory acuity to perform the rehabilitation program and the assessments in the Investigator's judgement.
	13.	Comfortable with the use of a smartphone. If assistance is required for the use of FeetMe technology, a caregiver or volunteer is fully available to assist the patient.
	14.	Willingness to be regularly contacted via phone-calls.
	15.	Willingness to suspend conventional physiotherapy treatment and start the FeetMe rehabilitation program, if applicable.
	16.	French speaker.
	Pat	ients must not fulfil the following criteria:
	Exe	clusion criteria
	1.	Medical history indicating a Parkinsonian syndrome other than idiopathic PD.
	2.	Unable to walk without walking aid or presence of an injury preventing the patient to walk.
	3.	Any relevant comorbidity or vestibular/visual dysfunctions limiting locomotion or balance.
	4.	Clinically significant comorbidities which in the judgement of the investigator may preclude the reliable gait assessment of the patient.
	5.	Patients with poor wound healing or broken skin on the feet.
	6.	Patients with foot implants.
	7.	Montreal Cognitive Assessment (MoCA) score $\leq 24/30$.
	8.	Patients with dementia.
	9.	Patients with apathy.

	10. Participation in another clinical trial with an investigational drug/ therapeutic within the three months before screening and during the study, unless agreed by the Sponsor.
	11. Patients who had Lee Silverman Voice Treatment (LSVT) Big therapy within the past 12 months or have it planned during the course of the study.
	12. Patients with Deep Brain Stimulation planned during the first 12 weeks of the study.
	13. Patients with pacemakers.
	14. Patients performing vigorous exercise > three times a week, 30 mins or more per session.
STUDY DESIGN AND ASSESSMENTS	This is a multicentre, controlled, randomised in two parallel-groups, open-label, study designed to evaluate the efficacy of FeetMe home- based self-rehabilitation program in comparison to conventional physiotherapy, including no physiotherapy in patients with PD. The study consists of a screening period, a primary intervention period of 12 weeks and a long-term intervention period of 12 weeks.
	Screening
	During their routinely scheduled visit at the investigational site patients who express interest in participating in the study will be introduced to the device. If judged to be comfortable with and interested in the technology, patients will return to their home to consider their participation. There is a reflexion period that lasts at least fifteen days up to one month If the patient decides to participate in the study, they return to the site for the screening visit. Once the informed consent is signed the screening assessments will be performed by the investigator (the neurologist). If eligible, the patients will be randomised either into the conventional physiotherapy (CPt control group) or the FeetMe rehabilitation program (experimental group).
	Primary Intervention Period
	Once randomised patients will proceed to the Baseline Visit (BL). At the BL visit, all participants (experimental and CPt control group) will be trained to use the FeetMe devices and will wear the insoles as much as possible throughout the visit. Standard gait and balance assessments will be performed (6 minute walk test (6MWT), MiniBESTest). Additionally, patients will perform multiple clinical assessments designed to assess: disease severity, gait, balance, mobility, etc. by completing different surveys.
	Following the BL visit, all patients will enter an initial 12 week period according to their patient group. Every patient in the study will be provided with a pair of insoles and will take the device to their homes. All patients, whatever the group of randomisation, will be asked to wear them as much as possible for 14 days after the BL visit to allow continuous gait data collection. This will permit the gathering of extensive data on a considerable number of gait parameters in a more familiar and natural setting reflecting real-life conditions. The FeetMe

patients will then continue to use the insoles according to the FeetMe rehabilitation program schedule.						
During the Primary Intervention Period (PIP), all patients will participate in two remote visits: Visit 1 (four weeks after BL) and Visit 2 (eight weeks after BL). During these visits, all patients will perform a short battery of self-reported questionnaires.						
At the end of the 12 week PIP, all patients will participate in a visit at their respective study centres (Visit 3). During the visit, they will perform the same gait and clinical assessments as during the BL visit allowing to record primary and secondary outcomes.						
Open Label Extension period						
Following Visit 3, patients will be asked whether they want to:						
a) continue with their already assigned treatment;						
Patients will continue with their respective rehabilitation programs.						
b) switch to the other arm;						
If patients on the conventional physiotherapy arm would like to start the FeetMe program they will be trained to use the devices and will start their 12 weeks program. Patients of FeetMe group wanting to switch from FeetMe to CPt will need to arrange the care themselves. Patients who switch will have the same visit schedule as during the first three months.						
c) discontinue rehabilitation.						
If a patient would like to discontinue rehabilitation they will still be asked to remain in the study for further data collection.						
At Visit 3 every patient will again be provided with a pair of insoles to take to their homes. All patients will be asked to wear them as much as possible for 14 days. Patients on the FeetMe arm will also use their device according to their program schedule.						
At the end of the second 12 weeks rehabilitation, all patients will participate in an additional in-clinic visit (Visit 4) at their respective study centres. During this visit, they will perform the same gait and clinical assessments as in the BL visit and Visit 3, wearing the insoles as much as possible throughout the visit. Following Visit 4, all patients will again take the insoles home to participate in an additional two-week remote gait monitoring.						
All assessments performed at the designated visits by the patient must be performed in the ON-State.						
Once the core 26 week period of the study is completed, an End of Study visit will be scheduled remotely and the patient's participation in the study will be considered concluded.						
Based on the emerging data, the Sponsor may decide to ensure that participants have the option to continue or take part in the FeetMe rehabilitation program. Such extension will be described in a separate document.						
Primary Endpoint						

	Change from baseline to Week 12 (Visit 3) in gait velocity (cm/s) assessed during the 6 Minutes Walk-Test (6MWT).
	Key Secondary Endpoint
	Change from baseline to Week 12 (Visit 3) in Stance Time Variability assessed during the 6MWT.
	Secondary Endpoints
	• Rate of falls at Week 12 based on the results of the falls diary.
	• Change from baseline to Week 12 (Visit 3) in the asymmetry of the swing duration assessed during the 6MWT.
	• Change from baseline to Week 12 (Visit 3) in the Mini-BESTest.
	• Change from baseline to Week 12 (Visit 3) in Unified Parkinson's Disease Rating Scale (MDS-UPDRS) Part III sub-score.
	• Change from baseline to Week 12 (Visit 3) in the results of the Parkinson Disease Questionnaire (PDQ-39).
	Exploratory Endpoints
	• Rate of falls at Week 24 based on the results of the falls diary.
	• Change from Baseline to Week 24 (Visit 4) and from Week 12 (Visit 3) to Week 24 in:
	- Gait velocity (cm/s) assessed during the 6MWT
	- Stance Time Variability assessed during the 6MWT
	- Asymmetry of the swing duration assessed during 6MWT
	- the Mini-BESTest
	- MDS-UPDRS Part III sub-score
	- the results of the PDQ-39
	 Change from Baseline to Week 12 (Visit 3) and to Week 24 (Visit 4) and from Week 12 to Week 24 in the:
	- gait parameters measured by the FeetMe Monitor during the 6MWTs other than ones of the primary and secondary endpoints
	- gait parameters measured by the FeetMe Monitor during remote gait monitoring
	- results of the pain VAS
	- results of the Parkinson Disease Sleep Scale 2 (PDSS2)
	- results of the Clinical and Patient Global Impression of Severity scales (CGI/PGI-S)
	- results of the Clinical and Patient Global Impression of Improvement scales (CGI/PGI-I)
	• results of the MDS-UPDRS I, II and IV sub scores
	• Actual versus prescribed time spent on physiotherapy at Week 12 and Week 24.
· · · · · · · · · · · · · · · · · · ·	

	• Results of the Patient and Investigator satisfaction questionnaire.
	• Number of device and protocol procedure related adverse events at Week 12 and at Week 24.
SAMPLE SIZE	N=150 The main objective of the RE-CONNECT study is to demonstrate the efficacy of FeetMe home-based rehabilitation program compared to conventional physiotherapy at Week 12 in PD patients. The primary endpoint is the change from baseline to Week 12 in gait velocity (cm/s) assessed during the 6 Minutes Walk-Test (6MWT). The sample size computation is based on the study of Chris J Hass et al. (Hass et, al, 2014.) aiming to determine the Minimal Clinically Important Difference (MCID) for the gait velocity in patients with idiopathic Parkinson's disease. In this study including 324 patients, MCID for gait velocity was classified as small, moderate and large with values of 6 cm/s, of 14 cm/s and 22 cm/s respectively (using a distribution-based analysis and the categorization defined by Cohen (Cohen et al, 1988)). We aim to show that the Feetme rehabilitation procedure will allow to improve the change in gait speed at least in a moderate range in
	Improve the change in gait speed at least in a moderate range in comparison with that in standard rehabilitation group and we set the difference to be detected at 14cm/s. In the Chris J Hass et al, the standard deviation of gait velocity was estimated at 27 cm/s. To detect a difference of 14cm/s between the two groups for the change in velocity with a standard deviation of 27 cm/s for the change from baseline to Week 12 in gait speed (assuming a conservative correlation coefficient of 0.5 between the measures at baseline and at week 12), 60 patients per group are needed (two-sided Student's test, type I error of 0.05 and a power of 80%). To take into account a 20% rate of drop out for the measurement of the gait velocity at week 12 (15% of lost to follow up and 5% of deaths or injuries), we plan to recruit 75 patients per group (a total of 150 patients).
STATISTICAL METHODS	The primary outcome (the change in the gait velocity between baseline and week 12, assessed during the 6 Minutes Walk-Test) will be estimated and compared between Feetme rehabilitation and conventional physiotherapy groups using the constrained longitudinal data analysis (cLDA) model proposed by Liang and Zeger, including centre as random effect and adjusted for the covariable "already in rehabilitation" considered as stratification factor in the randomisation. The between- group mean differences in 12-week change in gait velocity will be estimated by the time-by-arm interaction as treatment effect size. The assumptions of the cLDA model will be checked. We will use the analysis of cDLA model residuals by examining graphically the normality of residuals (histogram and Quantile-quantile plot) and by using the Shapiro Wilk test. In case of strong departure from the normality assumptions (even after applying a logarithmic transformation), nonparametric analysis will be used as recommended by Vickers et al.; absolute changes between baseline and 12-week will be calculated and compared between the 2 treatments groups using non-parametric analysis of covariance adjusted for baseline values. The effect size will be assessed by Hedges's g (standardized differences) computed on rank transformed data with its

	95% confidence interval (using the method based on noncentral Student distribution which is a corrected version of Cohen's d taking into account the sample size).				
BENEFIT/RISK CONSIDERATIONS	A risk analysis was carried out in accordance with ISO 14971 to identify the potential risks associated with the FeetMe Rehabilitation device. The residual risks are all at an acceptable level.				

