		- gait parameters measured by the FeetMe Monitor during the 6MWTs other than ones of the primary and secondary endpoints
		- gait parameters measured by the FeetMe Monitor during remote gait monitoring
		- results of the pain VAS
		- results of the Parkinson Disease Sleep Scale 2 (PDSS2)
		 results of the Clinical and Patient Global Impression of Severity scales (CGI/PGI- S)
		- results of the Clinical and Patient Global Impression of Improvement scales (CGI/PGI-I)
		- results of the MDS-UPDRS I, II and IV sub scores
To explore the compliance with acceptability, and patient's e throughout the study	training, Ac ngagement phy	ctual versus prescribed time spent on hysiotherapy
To explore the satisfaction with the ser-	vice Re sat	esults of the Patient and Investigator tisfaction questionnaire
To evaluate the safety of FeetMe h rehabilitation program.	ome-based Nu pla	umber of device and clinical investigational an procedure related adverse events.

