7.3 Baseline Visit

All randomised patients will participate in the Baseline Visit. This visit will be on the same day as the Screening Visit.

Patients will be instructed in the use of the FeetMe Monitor and wear the insoles for the duration of the visit, while performing a series of assessments.

The following assessments will be performed at the Baseline Visit:

CIP Number 2023-A00150-45 Final version 0.2

- Demographic data collection (month and year of birth; gender, weight, height, leg length, shoe size)
- Recording of relevant medical history, prior medications
- Gait Assessments, which must be performed in ON-phase:
 - 6 Minutes Walk Tests (6MWT)
 - Mini-BESTest

During the 6MWT and the Mini-BEST gait data will be recorded using the FeetMe Rehabilitation or Evaluation application. Specific instructions set out in the Site User Manual must be followed when setting up and executing the assessments.

- Disease specific rating scales:
 - The Movement Disorder Society sponsored Revision of the Unified Parkinson's Disease Rating Scale (MDS-UPDRS)
- Other Assessments:
 - Freezing of Gait Questionnaire (FOG-Q)
 - Parkinson Disease Sleep Scale 2 (PDSS2)
 - Pain VAS
 - Parkinson Disease Questionnaire (PDQ39)
 - Patient Global Impression of Severity (PGI-S)
 - Clinical Global Impression of Severity (CGI-S)

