 - Clinical Global Impression of Improvement / Patient Global Impression of Improvement (CGI/PGI-I)
- Potential adverse events and change in concomitant medication since the last contact.
- The source documents must be collected from the patients and the diary and tracker transcribed into the database.
- Also, the patients further allocation is to be decided (Section 7.4).
- At the end of the visit the patients will return home with their devices (as applicable based on their new or unchanged treatment) and proceed into the Remote Gait Monitoring 2 (Section 7.4.1).

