8.6.6 Clinical Global Impression of Severity (CGI-S)

The Clinical Global Impression of Severity is a standard clinician rating scale commonly used in Parkinsonism clinical trials, designed to assess the severity of symptoms of a patient (Guy, 1976). The CGI-S consists of a single assessment, scored on a scale ranging from 1 (normal/least severe symptoms) to 7 (most severe symptoms). The Investigator performs a medical examination and the scoring. The CGI-S takes around three minutes to complete.

The CGI-S will be performed at the Baseline Visit (Appendix R).

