8.6.7 Patient Global Impression of Severity (PGI-S)

The Patient Global Impression of Severity is a standard patient self-rated scale, designed to evaluate the severity of symptoms of a patient (Guy, 1976). The PGI-S consists of a single assessment, scored on a scale ranging from 1 (normal/least severe symptoms) to 7 (most severe symptoms). This assessment is self-administered by the patient. The PGI-S takes approximately three minutes to complete.

The PGI-S will be performed at the Baseline Visit (Appendix Q).

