14.17 Appendix Q – Patient global impression of severity (PGI-S) and improvement (PGI-I)

14.17.1 PGI-S : patient global impression of severity

A compléter à la visite Baseline

Veuillez mettre une croix en face de la réponse qui décrit le mieux votre état de santé actuel :

- o Pas de symptôme
- Très peu de symptômes
- Peu de symptôme
- Symptômes modérés
- o Symptômes légèrement sévères
- o Symptômes sévères
- Symptômes très sévères

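### The listed change in CGI-S and PGI-S cannot be formed from a Baseline-only schedule, and the CGI-I and PGI-I forms do not fit their stated scoring (exploratory endpoints, low severity)

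*Protocol*

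**What the plan says.** **Endpoints.** The exploratory endpoints in the Synopsis place "results of the Clinical and Patient Global Impression of Severity scales (CGI/PGI-S") under a stem covering three intervals: Baseline to Week 12, Baseline to Week 24, and Week 12 to Week 24. Table 5.1 repeats the entry: "results of the Clinical and Patient Global Impression of Severity scales". Both lists put CGI-I and PGI-I under the same stem.

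**Schedule of the severity scales.**
- The Baseline list in 7.3 includes "Clinical Global Impression of Severity (CGI-S") and its patient counterpart.
- Section 8.6.6 says "The CGI-S will be performed at the Baseline Visit (Appendix R"), and 8.6.7 says "The PGI-S will be performed at the Baseline Visit (Appendix Q").
- The PGI-S form in Appendix Q is headed "A compléter à la visite Baseline", and the CGI-S form in Appendix R carries the same header.
- Table 6.1 shows a single mark in the CGI-S / PGI-S row.

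**Later visits.** The Visit 3 list in 7.4.3 names "Clinical Global Impression of Improvement / Patient Global Impression of Improvement (CGI/PGI-I"), and the Visit 4 list in 7.5.3 names the same pair. Neither names a severity scale. General sentences point the other way: for Visit 3 the Synopsis says that "they will perform the same gait and clinical assessments as during the BL visit", and 7.4.3 and 7.5.3 open with similar wording.

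**Scoring of the improvement scales.** Section 8.6.8 gives CGI-I a range of 1 to 7, from greatly improved to greatly worse. Section 8.6.9 gives PGI-I a range of 1 to 4, with anchors that describe symptom severity. The forms in 14.17.2 and 14.18.2 each print six unnumbered options and ask about change since the *dernière visite*.

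**The concern.** A change score needs a value at both ends of the interval. If sites follow the itemised schedule, the severity scales have a value at one end only, and the listed endpoint has no data behind it. What is collected, and when, is fixed by the protocol and its forms. If change in severity really is wanted, a later analysis plan cannot supply Visit 3 and Visit 4 values that were never recorded.

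For the improvement scales the problem is scoring. Section 8.6 makes the paper form the source document and has scores entered in the eCRF. A site holding a six-option form without numbers cannot enter the 1 to 7 or 1 to 4 score that the text describes. The stem adds a further difficulty: an improvement rating already expresses change and has no Baseline value, so a change from Baseline in it is undefined when read literally.

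**Working it through.** No sample size, power or error rate is involved. The check sets the passages side by side and counts.

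**Severity scales: time points needed and scheduled**

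| Source | Baseline | Week 12 | Week 24 |
|---|---|---|---|
| Endpoint lists (Synopsis, Table 5.1): needed | yes | yes | yes |
| 7.3 list | yes | – | – |
| 7.4.3 list (Visit 3) | – | improvement scales only | – |
| 7.5.3 list (Visit 4) | – | – | improvement scales only |
| 8.6.6, 8.6.7 | yes | no | no |
| Form headers, Appendices Q and R | yes | no | no |
| Table 6.1 | one mark in the row | | |

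Listed contrasts: 2 scales × 3 intervals = 6. Time points needed: 3. Time points in the itemised schedule: 1. Each contrast needs two time points, so 0 of 6 can be formed.

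The table in the available text was extracted from a PDF and its column positions are not reliable. The conclusion does not rest on it, because the visit lists, the scale sections and the form headers each say Baseline independently.

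**Scales: text and form**

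| Scale | Range in text | Codes | Options on form | Agreement |
|---|---|---|---|---|
| CGI-S | 1–7 | 7 | 7 | yes |
| PGI-S | 1–7 | 7 | 7 | yes |
| CGI-I | 1–7, better to worse | 7 | 6 | no |
| PGI-I | 1–4, severity anchors | 4 | 6 | no |

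On both improvement forms the options split as 2 better + 1 unchanged + 3 worse = 6. CGI-I has one code more than options (7 − 6 = 1). PGI-I has two options more than codes (6 − 4 = 2), and its anchors describe severity, whereas the form asks about improvement or worsening.

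**Time cost of collecting severity later.** Sections 8.6.6 and 8.6.7 put each scale at about three minutes: 2 scales × 3 min × 2 visits = 12 minutes per patient.

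**The case against.** The strongest reply is that this is list placement and nothing more. Severity at Baseline followed by improvement ratings at Visits 3 and 4 is a sensible and common arrangement, and the scale sections, visit lists and form headers all describe it. The nesting of the exploratory list is loose elsewhere: MDS-UPDRS Parts I, II and IV form a separate bullet in the Synopsis but fall under the change stem in Table 5.1. If the severity bullet is misplaced, no intended data are lost. This stands as a probable explanation, and it is why the severity is low. It does not remove the contradiction, since both endpoint lists still promise a change that the schedule cannot give.

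A reader might infer from the general sentences about repeating the Baseline assessments that sites will collect different data, or that the severity scales are in fact scheduled. The documents give little support for either. In 7.4.3 and 7.5.3 the general sentence is followed by the list that itemises it, and that list omits the severity scales.

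Three stronger readings of the improvement forms are also tempting:
- **A fixed numerical shift in the unchanged category.** This needs print-order coding and a defined midpoint. Section 8.6.8 gives only the end anchors, and coding may be settled in the eCRF or the SAP.
- **Recall periods that differ between patients who switch and those who do not.** This needs patients to count remote contacts as the last visit, which no passage says. What stands is that the reference visit is not named.
- **A known effect of the uneven options on the comparison between arms, or known absence of one.** Nothing in the protocol allows either to be asserted.

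On CGI-I, an option lost in text extraction cannot be wholly excluded, although both forms show the same six. The PGI-I mismatch stands regardless, because four severity-anchored codes fit neither six nor seven improvement options.

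Finally, the stem can be read generously, with a Week 12 improvement rating taken as the Baseline to Week 12 result. That is fair as to intent, but the wording should say so.

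**Conclusion.** Wrong as written, at low severity. Under the itemised schedule 0 of the 6 listed CGI-S and PGI-S contrasts can be formed, and neither improvement form can be scored by the rule in its own section. The first result assumes that sites follow the itemised lists, scale sections and form headers, which agree with one another. The second rests on the six options printed in both appendices.

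The effect is confined to exploratory endpoints, which 9.2.6 and 9.5.3 leave to descriptive summary. A reader might infer a threat to the main results. There is none: the primary, key secondary and secondary endpoints, the testing hierarchy and the sample size do not use these scales. Nor do the documents show that intended data will be lost; that depends on whether the sponsor wants change in severity at all.

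**What to change.** **Severity scales.** Choose one option and make every section agree.
- Delete the CGI-S/PGI-S change endpoint from the Synopsis and Table 5.1 and keep the scales as Baseline descriptors. This costs patients nothing.
- Or add both scales at Visits 3 and 4 in Table 6.1, 7.4.3, 7.5.3, 8.6.6, 8.6.7 and the two form headers, at about 12 minutes per patient.

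**Improvement scales.**
- Make the number and anchors of the options agree between text and form, and number them. Seven options would fit the existing CGI-I text. For PGI-I the number is the sponsor's choice, but 8.6.9 needs improvement anchors in place of severity anchors.
- List the ratings as Week 12 and Week 24 results, outside the change stem.
- Replace *dernière visite* with one named reference visit that is the same for all patients. The last in-clinic visit would rate Baseline to Week 12 and Week 12 to Week 24 directly, which suits the objectives on patients who stop or switch at Week 12, but would give no direct Baseline to Week 24 rating. Baseline at both visits would give that rating but lose Week 12 to Week 24, and would ask for recall over 24 weeks.

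**Cost.** A small amendment to the protocol and forms, with resubmission to the ethics committee under 12.1. Ratings already made on the six-option forms would not be directly comparable with later ones, so the form version should be flagged in the database.
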